**Table 2. INSPIRE-ASP Pneumonia Trial Educational Binder and Distributed Material**

Topic	Description
1. Trial Summary	Goals and investigative team
2. Frequently Asked Questions	Answers to common questions about the trial or protocol.
3. Roles and Responsibilities	Description of expected roles and responsibilities of pharmacy and physician antibiotic stewardship champions
4. Talking Points	Talking points for common physician and pharmacist questions about the trial or protocol
5. Committee Protocol or Policy Proposal	Description of CPOE smart prompt antibiotic stewardship initiative for committee approval submission to adopt as hospital protocol or policy
6. Kick-Off PowerPoint	PowerPoint slides used in the kick-off webinar
7. Physician Education PowerPoint Presentations	Description of, and basis for, guidance on appropriate antibiotic use for pneumonia, definition of extended-spectrum antibiotic groups, the INSPIRE-ASP MDRO risk estimate and smart prompt, and compliance feedback reports.
8. Feedback	Process for study champions to feedback compliance reports to physicians

### **B.1.8 Intervention Phase Activities**

The automated point-of-care precision medicine CPOE smart prompts will be implemented at each facility randomized to the intervention arm. Automated compliance feedback reports detailing prescriber response to CPOE prompt recommendations will be generated on a rolling 3-month basis (or sooner if available), including reasons for continuing with extended spectrum antibiotic prescribing. Pharmacy/physician study champions will provide feedback to prescribers that show common and consistent deviation from CPOE smart prompt recommendations.

We will have a dedicated study email and toll-free number for study questions. Hospitals that are not represented on coaching calls will receive an email from core staff asking for their responses to polling questions and directing them to the recorded link of the coaching call.

For both study arms, study site champions will be required to confirm that a) no new hospital initiatives have been planned or implemented. If a site reports a new hospital antibiotic stewardship intervention that may represent a direct conflict with the INSPIRE-ASP Pneumonia trial, they will be asked to report the initiative to the trial Steering Committee for determination of trial conflict. Hospitals that implement interventions that conflict with the trial will be given the options of either not pursuing the conflicting intervention or dropping from the trial.

### **B.1.9 INSPIRE-ASP Pneumonia Trial Outcomes**

The goal of this trial is to reduce unnecessary physician prescribing of empiric extended-spectrum antibiotics (Table 8). Trial outcomes evaluating intervention effectiveness are outlined in **Table 3** and will be applied to the study population of adult patients who have an ICD-10 claims code indicating pneumonia is present on admission, who received any antibiotic within 3 days of admission, and who were admitted to a non-ICU location. For admissions initially on a non-ICU floor and transferred to the ICU, analysis will include only admission days on the non-ICU floor within 3 days of admission.

The primary trial outcome is defined as the summed number of different extended spectrum antibiotics received each day, measured repeatedly over the first three days of an admission and divided by the number of days of the admission within the empiric period. An empiric day is a day within the first three days of an admission. We define this outcome as an Extended-Spectrum Days Of Therapy (ES-DOT) per empiric day. Days of therapy (DOT) is specific to each extended-spectrum antibiotic, where any dose is considered one day's worth of therapy. The ES antibiotics are then aggregated to obtain the total ES DOT. For example, if a patient is started on vancomycin and cefepime for 1 day, this will count as 2 ES DOT for that day. Multiple

doses of the same antibiotic received on the same day are only counted as one day of therapy for that extended spectrum antibiotic. This outcome will include antibiotics in **Table 1**.

**Table 3: Primary and Secondary INSPIRE-ASP Pneumonia Trial Outcomes**

Outcome	Metric
Primary Trial Outcome	
Extended-Spectrum Days Of Antibacterial Therapy (ES-DOT) per Empiric Day	The summed number of different extended-spectrum antibacterials received each empiric day, measured repeatedly over the first three days of an admission and divided by the number of empiric days of the admission. An empiric day is a day within the first three days of an admission. 
Secondary Trial Outcomes	
Vancomycin Days of Antibacterial Therapy per Empiric Day	The summed number of days of Vancomycin received each empiric day per at-risk-day (first 3 days of admission) 
Antipseudomonal Antibiotic Days Of Therapy (ES-DOT) per Empiric Day	The summed number of different antipseudomonal antibacterials received each empiric day, measured repeatedly over the first three days of an admission and divided by the number of empiric days of the admission. An empiric day is a day within the first three days of an admission. 

E.g., if a patient is admitted for 2 days, ES-DOT will be calculated for 2 days and divided by 2 empiric days; conversely if a patient is admitted for 4 days, only the first 3 days will be evaluated.

Does not include aminoglycosides or fluoroquinolones.

Safety outcomes planned for the primary manuscript are shown in **Table 4**. Safety outcomes will be analyzed separately from the main effectiveness outcomes of the trial (see Primary Statistical Analysis section below).

**Table 4: Other Pre-Specified Outcomes – Safety Trial Outcomes**

Safety Trial Outcomes (other pre-specified outcomes)	
Antibacterial Escalations [Safety Outcome]	Days from start of standard-spectrum antibacterial until switch to extended-spectrum antibacterial during hospital stay
ICU Transfers [Safety Outcome]	Days from start of hospitalization until ICU transfer within hospital stay
Length-of-stay [Safety Outcome]	Days from hospital admission to discharge

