### B.1.10 Analysis

The primary trial outcome is defined as the summed number of different extended spectrum antibiotics received each day, measured repeatedly over the first three days of an admission and divided by the number of days of the admission within the empiric period. An empiric day is a day within the first three days of an admission. We define this outcome as an Extended-Spectrum Days Of Therapy (ES-DOT) per empiric day. For clarity the calculation is as follows: we define a DOT for a particular ES antibiotic as a day in which any number of doses of that antibiotic is given. Different ES antibiotics are summed across the empiric days for each patient admission, then divided by the empiric days for that patient-admission to determine each admission's DOT per at-risk day. If an admission is less than 3 days, only the number of days the patient is admitted will contribute to the numerator and denominator. Antibiotics given during an associated emergency department visit on the date of hospital admission are counted toward the ES-DOT of the first hospital day.

The main trial results will be based upon as-randomized, unadjusted analyses of admission-level ES-DOT per empiric day. We define ES-DOT per empiric day at the individual admission level so that we can perform analyses on individuals.

The trial will be assessed among the cohort of adult admissions who have an ICD-10 claims code indicating pneumonia is present on admission, who received any antibiotic within 3 days of admission, and who were admitted to a non-ICU location. For admissions initially on a non-ICU floor and transferred to the ICU, analysis will include only admission days on the non-ICU floor within 3 days of admission.

The trial periods are defined as follows: (1) Baseline – April 1, 2017 – September 30, 2018 (18 months); (2) Phase-in – October 1, 2018 – March 31, 2019 (6 months); (3) Intervention – April 1, 2019 – June 30, 2020 (15 months).

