The primary trial analysis will use an as-randomized unadjusted model with two-tailed significance set at alpha = 0.05. Secondary outcomes also will be assessed using an as-randomized unadjusted model with adjustment for multiple comparisons with two-tailed significance set at alpha = 0.025 for the two secondary outcomes. Subsequent analyses of the primary and secondary outcomes will include both as-treated and adjusted models. Adjusted models will account for individual characteristics such as age, gender, comorbidities, and prior history of MDROs as well as hospital characteristics such as hospital antibiotic resistance. We will also account for randomization unit and for seasonality. These analyses will be reported as point estimates with confidence intervals without p-value. The reason for including these analyses is to provide additional information related to the trial outcomes for readers to assess the effects of potential confounders. The reason to not include them in a formal multiple comparisons adjustment is because these analyses are non-independent evaluations relative to the as-randomized unadjusted analyses.

Safety outcomes noted in the below table will be assessed in the most conservative manner to identify potential safety issues. This is required because a reduction in ES-DOT might be achieved only by incorrectly withholding ES antibiotics when they were really needed. Each safety outcome will be evaluated for non-inferiority using an as-randomized unadjusted model with a one-tailed significance set at alpha = 0.05. Analyses planned for these assessments are proportional hazards models with random effects (to account for hospital effects). These models are sometimes called frailty or shared frailty models. Because these are safety outcomes, we do not intend to make adjustments for multiple comparisons in testing them, further increasing conservatism.

All analyses will be performed using current versions of SAS (Version 9.4, as of writing, SAS Institute, Cary NC) and/or R (Version 4.0, as of writing).

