Vancomycin Days of Antibacterial Therapy per Empiric Day	The summed number of days of Vancomycin received each empiric day per at-risk-day (first 3 days of admission) ¹		
Antipseudomonal Antibiotic Days Of Therapy (ES-DOT) per Empiric Day	The summed number of different antipseudomonal antibacterials received each empiric day, measured repeatedly over the first three days of an admission and divided by the number of empiric days of the admission. An empiric day is a day within the first three days of an admission. ^{1,2}		

¹E.g., if a patient is admitted for 2 days, ES-DOT will be calculated for 2 days and divided by 2 empiric days; conversely if a patient is admitted for 4 days, only the first 3 days will be evaluated.

²Does not include aminoglycosides or fluoroquinolones.

Safety outcomes planned for the primary manuscript are shown in Table 2. Safety outcomes will be analyzed separately from the main effectiveness outcomes of the trial (see Primary Statistical Analysis section below).

Table 2: Other Pre-Specified Outcomes – Safety Trial Outcomes

Safety Trial Outcomes (other pre-specified outcomes)	
Antibacterial Escalations [Safety	Days from start of standard-spectrum antibacterial until switch to extended-
Outcome]	spectrum antibacterial during hospital stay
ICU Transfers [Safety Outcome]	Days from start of hospitalization until ICU transfer within hospital stay
Length-of-stay [Safety Outcome]	Days from hospital admission to discharge

Primary Statistical Analysis

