The primary trial outcome is defined as the summed number of different extended spectrum antibiotics received each day, measured repeatedly over the first three days of an admission and divided by the number of days of the admission within the empiric period. An empiric day is a day within the first three days of an admission. We define this outcome as an Extended-Spectrum Days Of Therapy (ES-DOT) per empiric day. For clarity the calculation is as follows: we define a DOT for a particular ES antibiotic as a day in which any number of doses of that antibiotic is given. Different ES antibiotics are summed across the empiric days for each patient admission, then divided by the empiric days for that patient-admission to determine each admission's DOT per at-risk day. If an admission is less than 3 days, only the number of days the patient is admitted will contribute to the numerator and denominator. Antibiotics given during an associated emergency department visit on the date of hospital admission are counted toward the ES-DOT of the first hospital day.

The main trial results will be based upon as-randomized, unadjusted analyses of admission-level ES-DOT per empiric day. We define ES-DOT per empiric day at the individual admission level so that we can perform analyses on individuals.

The trial will be assessed among the cohort of adult admissions who have an ICD-10 claims code indicating pneumonia is present on admission, who received any antibiotic within 3 days of admission, and who were admitted to a non-ICU location. For admissions initially on a non-ICU floor and transferred to the ICU, analysis will include only admission days on the non-ICU floor within 3 days of admission.

The trial periods are defined as follows: (1) Baseline – April 1, 2017 – September 30, 2018 (18 months); (2) Phase-in – October 1, 2018 – March 31, 2019 (6 months); (3) Intervention – April 1, 2019 – June 30, 2020 (15 months).

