The primary trial analysis will use an as-randomized unadjusted model with two-tailed significance set at alpha = 0.05. Secondary outcomes also will be assessed using an as-randomized unadjusted model with adjustment for multiple comparisons with two-tailed significance set at alpha = 0.025 for the two secondary outcomes. Subsequent analyses of the primary and secondary outcomes will include both as-treated and adjusted models. Adjusted models will account for individual characteristics such as age, gender, comorbidities, and prior history of MDROs as well as hospital characteristics such as hospital antibiotic resistance. We will also account for randomization unit and for seasonality. These analyses will be reported as point estimates with confidence intervals without p-value. The reason for including these analyses is to provide additional information related to the trial outcomes for readers to assess the effects of potential confounders. The reason to not include them in a formal multiple comparisons adjustment is because these analyses are non-independent evaluations relative to the as-randomized unadjusted analyses.

Safety outcomes noted in the above table will be assessed in the most conservative manner to identify potential safety issues. This is required because a reduction in ES-DOT might be achieved only by incorrectly withholding ES antibiotics when they were really needed. Each safety outcome will be evaluated for non-inferiority using an as-randomized unadjusted model with a one-tailed significance set at alpha = 0.05. Analyses planned for these assessments are proportional hazards models with random effects (to account for hospital effects). These models are sometimes called frailty or shared frailty models. Because these are safety outcomes, we do not intend to make adjustments for multiple comparisons in testing them, further increasing conservatism.

All analyses will be performed using current versions of SAS (Version 9.4, as of writing, SAS Institute, Cary NC) and/or R (Version 4.0, as of writing).

Power Size/Sample Size Calculations

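### Antibacterial escalation is naturally defined only for admissions that start a standard-spectrum drug, a step the prompt is built to change, so randomisation does not protect its non-inferiority test

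*Protocol*

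**What the plan says.** Protocol Table 4 lists three safety outcomes. Escalation is "Days from start of standard-spectrum antibacterial until switch to extended-spectrum antibacterial during hospital stay"; SAP Table 2 repeats it ("Days from start of standard-spectrum antibacterial until switch to" an extended-spectrum drug). The other two run from a point that every admission has: ICU transfer is "Days from start of hospitalization until ICU transfer within hospital stay", and length of stay is counted from admission.

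The only population written for the trial is in Protocol B.1.10 and the SAP's Primary Statistical Analysis section. It consists of adults whose claims show pneumonia on arrival, with these further conditions: "who received any antibiotic within 3 days of admission, and who were admitted to a non-ICU location". It sets no condition on the class of the first antibiotic.

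For safety, Protocol B.1.10 states: "Each safety outcome will be evaluated for non-inferiority using an as-randomized unadjusted model", one-sided at 0.05, by proportional hazards with hospital random effects. The SAP says the same. Covariate-adjusted analyses are announced for other outcomes: "Subsequent analyses of the primary and secondary outcomes will include both as-treated and adjusted models".

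Protocol B.1.2 has the prompt fire, in intervention hospitals only, when an extended-spectrum drug is ordered for pneumonia in the first three days. It then recommends standard-spectrum drugs when the estimated risk of a resistant organism is low; the SAP's Background section puts the threshold at below 10%.

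**The concern.** An as-randomised comparison is fair because assignment cannot affect who is compared. Here it can. Whether an admission starts on a standard-spectrum drug is decided after the hospital has been assigned, and moving that decision is the purpose of the prompt. The intervention-arm starters may include patients who would have started an extended-spectrum drug under routine care, and the routine-care starters have no counterpart to them.

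If those patients differ in their propensity to escalate, the hazard ratio can depart from 1 with no harm, or conceal harm that exists. This matters because Protocol B.1.10 justifies the safety outcomes by the possibility that extended-spectrum use falls through wrongly withholding needed drugs, and escalation is the outcome closest to that mechanism.

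**Working it through.** **Step 1. Who can be analysed.** Set the outcome definition beside the cohort definition. An admission given only extended-spectrum drugs is in the cohort but has no start time for escalation. A switch from standard to extended spectrum presupposes a standard-spectrum start. The definition thus largely implies an analysis among standard-spectrum starters, although neither document says so or says how extended-spectrum starters and same-day starts are coded.

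**Step 2. Is membership fixed before assignment?** No. Hospitals are the unit of randomisation (Protocol B.1.1), and the prompt acts later, on individual orders, in one arm.

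**Step 3. Does the planned model deal with it?** Hospital random effects address clustering, not which patients enter the comparison. A contrast with the baseline period is not written for the safety models. It would not help in any case, because the prompt changes selection only in intervention hospitals during the intervention period.

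**Step 4. How large could it be?** The plan has no figure to reproduce: it gives no share starting standard-spectrum, no share moved, no escalation rate and no non-inferiority margin. What follows is an illustration with every input assumed and no effect on any patient's own risk.

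Let p be the share of intervention-arm starters who are there only because of the prompt, and r their escalation hazard relative to usual starters. At time zero:

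HR = (1 − p) × 1 + p × r = 1 + p(r − 1).

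For example, p = 0.15 and r = 2 give 1 + 0.15 × 1 = 1.15.

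Over follow-up, the Cox estimate was found by solving the expected score equation with constant hazards, equal arms, no frailty term, and 10% or 30% cumulative escalation among usual starters.

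| p | r | HR at time zero | Cox HR, 10% escalation | Cox HR, 30% escalation |
|---|---|---|---|---|
| 0 | any | 1.00 | 1.00 | 1.00 |
| any | 1 | 1.00 | 1.00 | 1.00 |
| 0.05 | 0.5 | 0.975 | 0.974 | 0.973 |
| 0.05 | 2 | 1.05 | 1.048 | 1.043 |
| 0.10 | 0.5 | 0.95 | 0.949 | 0.946 |
| 0.10 | 2 | 1.10 | 1.096 | 1.086 |
| 0.15 | 0.5 | 0.925 | 0.923 | 0.919 |
| 0.15 | 2 | 1.15 | 1.144 | 1.130 |

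**Step 5. Can p be gauged from trial data?** If the prompt moves patients only towards standard-spectrum starts, p ≈ (q1 − q0)/q1, where q1 is the intervention-arm share starting standard-spectrum and q0 the share expected without the prompt. With q0 = 0.50 assumed, q1 = 0.50, 0.525, 0.55 and 0.59 give p = 0, 0.048, 0.091 and 0.153. A table of starts by arm and period would therefore let a reader judge p.

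**Step 6. Can p be near zero?** Yes. Protocol B.1.9 counts vancomycin plus cefepime on one day as 2 ES-DOT. Dropping one of the two halves that day's count without anyone becoming a standard-spectrum starter.

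**The case against.** The strongest reply is that the documents already give the time origin, the event and the window, and that the cohort is written elsewhere. A switch can occur only after a standard-spectrum start, so who is at risk is largely implied. That stands. A reader might infer that the outcome has no defined risk set at all; the text does not support that. What is missing there is coding detail, which alone would be a minor request. The selection problem, however, arises on precisely this natural reading.

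Second, no consequence is shown. That also stands. Every input in the illustration is assumed, p may be near zero, and without a margin no shift can be set against a decision threshold. If moved patients escalate more (r above 1), non-inferiority becomes harder to show, which is the cautious direction; only r below 1 assists a false pass. A reader might infer that the bias hides harm, or that a safety conclusion would change. The documents support neither.

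Third, escalation among patients given standard-spectrum drugs is a sensible clinical question, and no alternative is free of fault. A whole-cohort analysis timed from admission rises mechanically when the prompt works. Suppose half of admissions start extended-spectrum, 12.5% of those are moved, and 10% of all standard-spectrum starters escalate. Counting the remaining extended-spectrum starters as non-events gives 0.5 × 0.10 = 5.0% against 5.0% + 0.5 × 0.125 × 0.10 = 5.6%, a ratio of 1.125 with no harm. This is a good reason not to ask for that analysis. It does not make the comparison among starters a randomised one.

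Finally, the documents do not rule out adjusted safety models; they merely announce adjusted models for the primary and secondary outcomes only.

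**Conclusion.** The point holds for one of the three safety outcomes. As naturally read, the planned escalation test compares groups formed after assignment by a step that the intervention is designed to change, and so it lacks the protection that an as-randomised analysis implies. The conclusion rests on that reading of the outcome definition and on the prompt's stated function, not on any assumed number.

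The size and direction of bias are not derivable. Under the assumptions above, the follow-up hazard ratio without true harm lies between 0.92 and 1.14 at p = 0.15, between 0.97 and 1.05 at p = 0.05, and at 1.00 if nobody is moved or moved patients escalate like usual starters.

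It would be tempting to extend this to the trial's safety evidence generally, or to its main result. The documents do not support that: ICU transfer and length of stay are timed from hospitalisation or admission, and trial success rests on the arm-by-period term for the primary outcome.

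**What to change.** - Beside the escalation result, report the share of admissions starting a standard-spectrum drug, by arm and period.
- Add, as a sensitivity analysis, an escalation model adjusted for the covariates already named in Protocol B.1.10 and the SAP (such as age, gender, comorbidities, prior resistant organisms and hospital resistance).
- Describe the escalation result as a comparison among standard-spectrum starters that is subject to post-assignment selection, not as a randomised non-inferiority conclusion. Rest randomised safety conclusions on ICU transfer and length of stay.
- In the same text, state how extended-spectrum starters and same-day starts are coded.

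The cost is a few sentences in the SAP, one descriptive table and one additional model on covariates already planned. The real downside is that the conclusion on the outcome closest to the prompt's mechanism becomes weaker. Adjustment may also leave residual selection, since the named covariates include no explicit measure of severity at admission.

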### **B. INSPIRE-ASP Pneumonia Trial Study Design & Population**

#### **B.1.1 INSPIRE-ASP Pneumonia Trial Study Design & Population**

The INSPIRE-ASP Pneumonia Trial is a two-arm cluster-randomized trial in HCA hospitals comparing routine empiric antibiotic prescribing for patients admitted with pneumonia to prescribing informed by point-of-care precision medicine computerized physician order entry (CPOE) smart prompt for adult patients admitted to general medical or surgical floors. The unit of randomization will be the hospital. The trial will begin with a six-month phase-in period from October 1, 2018-March 31, 2019, followed by a 15-month trial intervention period between April 1, 2019-June 30, 2020. For analysis purposes, the cohort will be defined as adult patients with a primary or secondary claims code indicating pneumonia that is present on admission, did not transfer directly from the ED to ICU, and is treated with an antibiotic within the first 3 days of hospitalization. A baseline period between April 1, 2017-September 30, 2018 will be utilized for comparison with the intervention period at each hospital. Per guidance from the Office for Human Research Protections (OHRP), prisoners will not be included in this trial. Prescribers and antibiotic stewardship teams in intervention facilities will be trained (e.g., coaching calls, usual communication channels (email, flyers)) that prisoners should be excluded from the trial (i.e., the CPOE smart prompt should not be acted upon for these individuals). Data for any prisoners that may be inadvertently included in study datasets will be removed prior to analyses using claims data as well as admission/discharge/transfer codes indicating 'Court/Law Enforcement'.

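### No planned safety outcome counts in-hospital death as harm, and the handling of death is unspecified, so a rise in floor deaths could go unseen

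*Protocol*

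**What the plan says.** Protocol Table 4 and SAP Table 2 list the same three safety outcomes:

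- Escalation: "Days from start of standard-spectrum antibacterial until switch to extended-spectrum antibacterial during hospital stay".
- ICU transfer: "Days from start of hospitalization until ICU transfer within hospital stay".
- Length of stay: "Days from hospital admission to discharge".

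Protocol B.1.10 sets the test: "Each safety outcome will be evaluated for non-inferiority using an as-randomized unadjusted model with a one-tailed significance set at alpha = 0.05". The SAP section on the primary statistical analysis says the same. Both documents name proportional hazards models with a random effect for hospital. Both give the reason for testing safety: extended-spectrum use could fall because needed drugs were withheld. For that reason the outcomes "will be assessed in the most conservative manner to identify potential safety issues".

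Neither document limits discharge to discharge alive, gives a censoring or competing-risk rule, or lists death as an outcome or as part of a composite. Mortality is mentioned only in the protocol's background (A.1.3 and A1.7). No non-inferiority margin is stated.

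**The concern.** Death is the gravest result of the failure that the safety analysis is meant to catch. A patient who dies on the ward without an ICU transfer leaves all three analyses without being recorded as harmed. For length of stay, an unqualified discharge makes the death an event, and an earlier event is the favourable direction. For ICU transfer, and for escalation if no switch has occurred, observation stops with no event.

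At stake is whether three non-inferiority results could be reported as reassurance while floor deaths had risen in the intervention arm.

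**Working it through.** The plan gives no event rate, margin, power or sample size for the safety outcomes, so there is no figure of its own to reproduce. All rates below are assumptions. Hazard ratios (HR) are intervention over routine care. For length of stay the event is discharge, so HR above 1 is favourable; for ICU transfer, HR above 1 is unfavourable.

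**Step 1. Deaths replace live discharges at the same time.** Assume both arms share one stay-length distribution, with density f and cumulative distribution F. A proportion m die, 3% v 4%, and all extra deaths occur on the floor.

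- Deaths counted as discharges: the hazard is f/(1 − F) in both arms, so HR = 1.00.
- Deaths censored: the hazard is (1 − m)f/(1 − F), so HR = 0.96/0.97 = 0.990. For 3% v 4.5% it is 0.955/0.97 = 0.985.
- Deaths kept in the risk set as never discharged: the ratio varies over time. Cox fits to 200,000 simulated stays per arm (gamma, mean about 6 days) gave 0.96 to 0.965, and 0.95 to 0.956 for 3% v 4.5%.
- ICU transfer as written, 5% in both arms: simulated HR 0.99 to 1.00.

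**Step 2. ICU transfer or death, whichever first.** Let s be the share of control deaths that follow an ICU transfer, and d the extra floor deaths in percentage points. The risk ratio is [5 + 3(1 − s) + d] / [5 + 3(1 − s)].

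- d = 1: 9/8 = 1.125 at s = 0, and 6/5 = 1.20 at s = 1. Simulated HR: about 1.12 to 1.19.
- d = 1.5: 9.5/8 = 1.19 at s = 0, and 6.5/5 = 1.30 at s = 1. Simulated HR: about 1.17 to 1.30.

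**Step 3. Extra deaths shorten stays.** Now assume constant daily hazards, L for live discharge and D for death, with D multiplied by R in the intervention arm. With deaths counted as discharges, HR = (L + R·D)/(L + D) = 1 + m(R − 1), where m = D/(L + D).

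| Baseline mortality m | R = 1.5 | R = 2 |
|---|---|---|
| 2% | 1.01 | 1.02 |
| 4% | 1.02 | 1.04 |
| 6% | 1.03 | 1.06 |
| 8% | 1.04 | 1.08 |

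At m = 4% and R = 2, a live-discharge HR of 1 − 0.04/0.96 = 0.958 would be fully hidden. With deaths censored, the length-of-stay HR stays at 1.00 when floor deaths double.

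**Step 4. Which routes of harm are seen.** A simulation moved patients from the floor to live discharge, death or ICU at assumed daily hazards of 0.2, 0.006 and 0.012, with deaths counted as discharges and no hospital clustering. Control mortality was 4.1%.

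| Change in intervention arm | Mortality | Length-of-stay HR | ICU HR |
|---|---|---|---|
| Floor-death hazard doubled | 6.7% | 1.03 | 1.00 |
| Extra floor deaths replace ICU transfers (0.009 and 0.009) | 5.2% | 1.02 | 0.75 (= 0.009/0.012) |
| Death hazard in the ICU doubled | 5.0% | 1.01 | 1.00 |
| ICU transfer hazard × 1.5 | 4.7% | 0.99 | 1.50 |

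With 5,000 admissions per arm and an assumed margin of 1.05, doubling floor deaths raised the length-of-stay pass rate from 78% to 99%. The ICU pass rate at an assumed margin of 1.20 stayed at about 68-70%. In the last row the ICU test passed in 0% of runs at each assumed margin (1.05, 1.10, 1.20).

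No calculation was made for escalation.

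**The case against.** The strongest reply is that the documents are silent on death. They give one-line metrics and a model class, and an analyst could reasonably censor deaths. That is right. A reader might infer that the plan lays down a rule scoring death as a good outcome; it does not. Counting death as discharge is the plain consequence of the wording, not an instruction. The reply does not remove the problem, because under censoring the length-of-stay HR is 0.985 to 1.00 in these examples, so the deaths still barely show.

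A reader might also infer that extra deaths push all three tests towards non-inferiority. Neither the documents nor the arithmetic support this. In Step 1 the length-of-stay and ICU ratios stay near 1.00, and in Step 3 the length-of-stay shift is modest. The ICU hazard falls only where a floor death replaces a transfer. A death after transfer has already counted as an ICU event, and harm that acts through more transfers is detected.

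Two further points stand. The composite ratios depend on the share of control deaths that follow transfer, so only a range can be given. With no margin stated, passing is undefined in the plan, and the pass rates only illustrate direction; even a length-of-stay HR of 0.965 might pass under some margins.

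**Conclusion.** The concern holds as a blind spot. Whether deaths are coded as discharges or censored, the three written outcomes do not show a rise in floor deaths materially as harm. That conflicts with the plan's own aim of a conservative safety assessment. Favourable bias is real but secondary: a length-of-stay HR of 1.02 to 1.08 if deaths double and count as discharges, and an ICU HR below 1 only where deaths displace transfers.

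The sizes rest on assumed mortality of 2-8%, ICU transfer of about 5%, and extra deaths without prior transfer. The finding that no outcome counts death rests on the documents alone. It should be corrected, since the change is cheap and bears on the reassurance that the trial can give.

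**What to change.** In the SAP:

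1. Define the length-of-stay event as discharge alive, and keep in-hospital deaths in the risk set as never discharged (a subdistribution hazard).
2. Analyse ICU transfer or in-hospital death, whichever comes first, and show each component by arm.
3. Treat death before a switch as a competing event for escalation.
4. Report in-hospital death by arm as a safety outcome in its own right.
5. State the non-inferiority margin for each test, so that a pass is defined.

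The cost is SAP wording and a little more analysis. Protocol B.1.1 already plans to remove prisoners "using claims data as well as admission/discharge/transfer codes", so discharge disposition should identify deaths without new collection. That is an inference, because the passage does not mention death. The SAP is dated June 3, 2020, before the intervention period ends on June 30, 2020. The downside is that the composite mixes two kinds of event, so it should not be reported without its components.
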